injected. If both eyes have the same acuity the eye with longest onset will be injected. If one eye has <12 months and >6month since onset and the difference in acuity between the eyes is ≤ 10 letters, the eye with ≥ 12 months will be injected. If eyes have an acuity difference >10 letters, the eye with worse acuity will be injected.

Aim 2. To Evaluate the Safety of AAV-ND4 in subjects with acute (<12 months) bilateral loss of visual acuity to ≤ 35 ETDRS letters (Snellen = 20/200) (Group 2). The eye with worse acuity will be injected.

Aim 3. To Evaluate the Safety of AAV-ND4 in subjects with unilateral loss of acuity to ≤ 35 ETDRS letters, but who have “good acuity” ≥ 70 letters (20/40 Snellen) in the contralateral eye (Group 3). The eye with better acuity will be selected for injection.

For each group, administration of study drug will follow an adaptive plan to identify the maximum tolerated dose. If none of the three subjects at a given dose level develops a major toxicity, the next cohort will receive the next higher dose. We will wait a minimum of 6 weeks between injections of the same dose in successive subjects, and will wait until 3 months after the last subject is injected with this dose before moving to the cohort receiving the next higher dose. We will test the lowest dose first in 3 subjects of Aim 1, before moving on to testing this low dose in Aim 2, then lastly in Aim 3. Safety will be monitored for loss of 15 letters in Aims 1 and 2, but a difference of 15 letters worse in the treated eyes relative to untreated eyes for Aim 3. If acuity, and visual field testing demonstrate no toxicity in Aims 1 and 2, we will proceed with Aim 3.

The **objective** of this proposed clinical trial is to evaluate the safety of mitochondrially targeted ND4 gene therapy with the adenoassociated viral vector in appropriate LHON patients in a Phase I clinical trial. If warranted by the results of the Phase I trial, another aim will be to obtain a preliminary estimate of the therapy’s efficacy. We provide a summary of the extensive preclinical testing in relevant rodent animal models to support the efficacy of the approach proposed in this clinical trial.

The **primary hypothesis** being tested is there will be no systemic toxicity or loss of vision to No Light Perception in the injected eye.

4) **Background***

Background and Significance

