9. History of neurodegenerative conditions (e.g. multiple sclerosis, neuromyelitis optica, Parkinson disease)
10. History of autoimmune conditions (e.g. systemic lupus erythematosus)
11. Systemic diseases having ocular manifestations likely to confound assessment of study resultsHistory of cancer within five years other than localized basal or squamous cell carcinoma not near the orbital area. Patients with a prior history of cancer will need documentation from their cancer specialist that the cancer was cured at least 5 years before study entry.
12. Allergy to pupil dilating drops or narrow angles precluding safe dilation.
13. No Light Perception (NLP) vision in either eye.

, “No special populations are to be included in this research, such as children 14 years old or younger, prisoners, or pregnant women.

- **Exclude:** All subjects who are unable to consent
- **Exclude:** Children 14 years old or younger
- **Exclude:** Pregnant women

- **Exclude:** Prisoners

6) **Number of Subjects***

Number of Study Centers: One (1), Bascom Palmer Eye Institute, University of Miami, Miami, FL.

For each group patient recruitment will consist of 3 cohorts, until the last cohort which will consist of both Group I and III individuals.

Table 1 Proposed Sample Size

	Low-dose (1.18×10^9 vg)*	Medium dose (5.81×10^9 vg)*	High dose (2.40×10^{10} vg)	Higher dose (1×10^{11} vg)
Group I	3	3	3	
Group II	3	3		3
Group III	3	3		
Group I And** Group III				3 3

*=based on CHOP titers as recommended by FDA

As summarized above, dose escalation will follow the adaptive Phase 1 plan of Rubinstein and Simon (<http://linus.nci.nih.gov/techreport/phaselctd.pdf>). At each dose, escalation will occur until 2 of 3 (or 6) injected eyes manifest the safety endpoint. (See reference for detailed description of dose escalation strategy) Table 2 of the reference contains operating characteristics of this approach. Following the algorithm of Rubinstein and Simon with three doses, the sample size could range between 3 and 18 for each group. As an example, if the true probabilities of noteworthy safety events in the proposed three doses were 0.05, 0.25, 0.5, respectively, the most likely sample sizes for each group would range between N=9 with probability 20%, N=12 with probability 54%, or N=15, with probability 22%. These sample sizes could potentially be sufficient to observe a treatment effect when compared in a matched fashion to the uninjected eyes in groups 1 and 3.

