**Escalation from high dose group I to higher dose group II was previously approved. Since chronic bilateral group I individuals are considered at lower risk than group II, there are no additional safety concerns to injecting group I intermixed with group III individuals, after the 3rd group II injection and 3 month safety period. In this combined cohort, each of the 6 injections will be spaced at least 6 weeks apart. Ordering of participants will be determined by their presentation to the study and PI discretion, with the aim of ensuring injection of the more difficult to recruit group III individuals.

7) **Study-Wide Recruitment Methods* N/A for Multi-center trial**

Number of Study Centers: One (1), Bascom Palmer Eye Institute, University of Miami, Miami, FL.

Phase I. A review of the LHON patients currently being seen by [REDACTED] and [REDACTED] with long-standing severe vision loss of 20/200 or worse, shows that we have 23 patients who would be eligible for the Phase 1 study in Groups 1 and 2. We expect that the availability of a potential treatment will draw more patients in groups 2 and 3. Thus, we should have a sizable pool of patients for the Phase 1 safety study of the AAV-ND4 vector.

Individuals who have been diagnosed with G11778A mutation associated Leber's hereditary Optic Neuropathy and who are eligible based on inclusion and exclusion criteria will be invited to participate in this clinical trial. A complete physical examination and clinical chemistries will be performed at a pre-treatment, screening evaluation to further determine eligibility. Subjects will be considered enrolled when they sign the Informed Consent.

Enrollment Procedures:

Eligibility will be assessed at a study team meeting prior to the baseline 2 exam. This meeting must include at least one MD coinvestigator in addition to the PI. Other participants may include clinical staff, biostatistics center staff, and the CRORS office. Minutes will be recorded during these meetings and a sign in sheet will be kept. If the injecting retina specialist is unable to attend the assessment meeting, they will be asked to review and sign off on the eligibility criteria checklist prior to the injection. If the patient meets all inclusion and exclusion criteria a request will be forwarded to the research pharmacist for Study Drug dilution.

8) **Study Timelines***

- The duration of an individual subject's participation in the study:10 years

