- The duration anticipated to enroll all study subjects: 3 years
- The estimated date for the investigators to complete this study (complete primary analyses): 5 years after first patient has received administration of study agent.

9) **Study Endpoints***

Assessment of Primary Endpoint – Toxicity

The **primary safety endpoint** in this trial is the standard ocular examination. Toxicity will also be assessed by measurement of vision, hematology and serum chemistries, assays for vector genomes, reported subject history of any symptoms and adverse events.

Ocular. Routine eye examinations will be performed before and after vector administration, and surgeons administering the injections will be alert to injection administration related complications. The clinical ocular examinations for toxicity will include slit lamp examination, measurements of intraocular pressure (applanation tonometry or Tono-pen) and gonioscopy (as needed in cases of increased intraocular pressure to examine for anterior chamber abnormalities). Some potential ocular toxicities are included in Table 6-6 below. These are modifications of the Ocular/Visual Adverse Events tables of the Common Terminology Criteria for Adverse Events v3.0 (CTCAE), considering the LHON patient population and the circumstances of the intervention. Direct and indirect ophthalmoscopy and biomicroscopy will be the mainstay of the retinal examinations. Fundus photography (with infrared illumination) will also be taken to document fundus appearance.

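### The written condition for opening Group III names only acuity and visual field, and nothing requires a hold on Group III when non-visual toxicity occurs in Groups I or II at that dose

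*Combined protocol and SAP*

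**What the plan says.** Section 3 (Objectives) gives the order of the groups at the low dose. Three Aim 1 subjects are treated "before moving on to testing this low dose in Aim 2, then lastly in Aim 3". It then states the condition for the last step: "If acuity, and visual field testing demonstrate no toxicity in Aims 1 and 2, we will proceed with Aim 3". The sentence just before that condition sets the vision threshold, a 15-letter loss in Aims 1 and 2.

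The protocol's own definitions of safety are wider. Section 9 says that the primary safety endpoint "in this trial is the standard ocular examination", and it adds vision, laboratory tests, vector-genome assays, symptoms and adverse events. The primary hypothesis in section 3 is that "there will be no systemic toxicity or loss of vision to No Light Perception in the injected eye". Tables 6-6 and 6-7 grade ocular and systemic toxicity from 1 to 4.

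Two rules govern dose escalation. Section 3, for each group: "If none of the three subjects at a given dose level develops a major toxicity, the next cohort will receive the next higher dose". Section 6: "At each dose, escalation will occur until 2 of 3 (or 6) injected eyes manifest the safety endpoint".

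For the higher dose, the note to Table 1 in section 6 allows a combined cohort of 3 Group I and 3 Group III subjects "after the 3rd group II injection and 3 month safety period". Injections are at least 6 weeks apart. On sequence it says: "Ordering of participants will be determined by their presentation to the study and PI discretion".

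Section 12 has the Biostatistics Center report systemic, ocular and acuity-loss safety events to the FDA, NEI and DSMC. It also says that monitoring results are used to decide on continued recruitment. Section 13 gives the DSMC power to terminate the study.

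**The concern.** The condition for injecting a patient's better-seeing eye is narrower than the trial's own account of toxicity. Several risks described in section 4 are found by examination or blood tests, not first by a vision test: inflammation, immune response, cataract, raised pressure and retinal detachment. Such an event in a Group I or II subject may leave acuity and field unchanged when it is found. The written condition for Group III would then be met.

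The matter weighs more at the higher dose. Table 1 gives Group III no high-dose cohort, so at the higher dose it leans on what was seen in the other groups. Because order within the combined cohort is left open, a Group III eye could be injected when only the 3 Group II eyes have received that dose.

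**Working it through.** The plan gives no figure to reproduce on this point. The check sets the rules side by side and asks which of them would hold Group III after a non-visual event in Groups I or II at the same dose.

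**Counts**
- Group III planned subjects (Table 1 in section 6; dose table in section 12): 3 low + 3 medium + 3 higher = 9.
- Subjects treated at the low dose before Group III opens (section 3 order, Table 1 numbers): 3 Group I + 3 Group II = 6.
- Subjects required at the higher dose before a Group III injection (note to Table 1): 3, all Group II.
- Group III's own step from medium to higher: 1×10^11 / 5.81×10^9 = 17.2-fold. This is context for its reliance on other groups' data. Skipping the high dose is a separate design matter.

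**Worked case at the higher dose.** Suppose 1 of the 3 Group II eyes develops a Grade 3 uveitis (Table 6-6), with acuity and field unchanged.

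1. *Condition for Aim 3 (section 3).* It looks at acuity and field. Neither shows toxicity, so the condition is met.
2. *Major-toxicity rule (section 3).* It decides whether the next cohort receives the next higher dose, group by group. For Group III it looks back at Group III's own 3 medium-dose subjects. It does not look across to Group II at the higher dose, and no dose above that remains to be withheld from Group II. The term is not defined.
3. *Count of 2 of 3 (or 6) (section 6).* Even if the uveitis counts as the safety endpoint, the count is 1, which is below 2. A systemic event is not plainly counted, because the unit is the injected eye.
4. *Three-month safety period (section 6).* Time passes. No outcome or pass mark is stated.
5. *Reporting and review (sections 12 and 13).* The event goes to the FDA, NEI and DSMC. Any of them may act. No hold and no deadline is written. The DSMC's guaranteed minimum is two meetings a year, with calls as needed.

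No rule in steps 1 to 4 stops the Group III injection. Step 5 may stop it, by discretion.

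**The same case at the low dose.** With 1 such event among the 6 Group I and II eyes, step 1 again says proceed and the count of 2 is again not reached. The major-toxicity rule does not address the move, because Group III opens at the same dose, not a higher one. The three-month wait in section 3 applies before the next dose, so the only written interval here is the 6 weeks between subjects at one dose.

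**The case against.** The strongest reply is that non-visual toxicity is already covered. Section 12 requires ocular and systemic safety events to be captured and reported to the FDA, NEI and DSMC. The DSMC reviews them on an ongoing basis, recruitment decisions draw on that review, and the section says that statistical considerations serve only as guidelines. This stands. A reader might infer from the narrow condition that non-visual events go unmonitored, or could not stop Group III. The documents do not support that. Referral to the DSMC already exists; a required pause does not.

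Second, the major-toxicity rule applies to each group and is not limited to vision, so it covers Group III's own step from medium to higher. This also stands. It would be wrong to say that no non-visual criterion of any kind bears on Group III. The gap concerns toxicity in the other two groups.

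Third, a sympathetic reader could take the safety endpoint in section 6 to be the ocular examination of section 9, take the three-month period to cover all section 9 assessments, and treat the Aim 3 sentence as necessary but not sufficient. These readings are possible, but the text does not state them. Even on the first, a single event stays below the count of 2.

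Fourth, section 6 defers escalation detail to a cited reference, and sections 21, 22 and 32 refer to a manual of procedures. Neither is in the documents, and either could hold a criterion. That is a real limit.

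**Conclusion.** The point holds in a limited form. The stated condition for moving from Aims 1 and 2 to Aim 3 omits the primary safety endpoint and one part of the primary hypothesis. The higher-dose waiting period names no outcome. No section requires Group III injections to be held when non-visual toxicity occurs in Groups I or II at that dose.

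The size is modest. The plan gives no event rate, so no probability is claimed. Group III plans 9 subjects in all. This version is dated February 2019, and its note to Table 1 describes escalation to the higher dose in Group II as already approved. The earlier steps may therefore be past, leaving the 3 higher-dose Group III subjects as the live reach.

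A reader might also infer that vision tests say little in eyes that already see poorly. That is not part of this point: section 10 grades acuity below the chart through count fingers, hand motions and light perception. The gap lies in outcomes that are not vision tests.

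The conclusion assumes that neither the manual of procedures nor the cited reference contains the missing hold. It is a cheap improvement to a written rule, not evidence that subjects are unprotected.

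**What to change.** Reword the section 3 sentence so that Aim 3 proceeds at a given dose if acuity, visual field, ocular examination and systemic assessment show no toxicity in the Aim 1 and 2 subjects treated at that dose. Leave the existing acuity and field criteria as they are.

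Add the hold. If a Grade 3 or higher event on Table 6-6 or Table 6-7 occurs in those subjects, and is at least possibly related to the vector or the injection, Group III injections at that dose wait until the DSMC has reviewed it and agreed to proceed. This makes the rule a review, not an absolute bar, and an unrelated illness does not trigger it.

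In the note to Table 1, apply the same hold to the three-month safety period after the third Group II injection, and to any Group I subject already injected in the combined cohort.

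The cost is one sentence and one clause. No visit, test or subject is added: the examinations, laboratory tests and adverse event recording are already scheduled in Table 6-4, and the grades exist. The downside is possible delay in a group that section 6 describes as harder to recruit.

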An Open-label Dose Escalation Study of an Adeno-associated Virus Vector (scAAV2-P1ND4v2) for Gene Therapy of Leber's Hereditary Optic Neuropathy (LHON) caused by the G11778 mutation in mitochondrial DNA.

NCT02161380

Date: February 9, 2019. IRB 20140248.

1) **Protocol Title**

An Open-label Dose Escalation Study of an Adeno-associated Virus Vector (scAAV2-P1ND4v2) for Gene Therapy of Leber's Hereditary Optic Neuropathy (LHON) caused by the G11778 mutation in mitochondrial DNA

SHORT TITLE: Leber's hereditary optic neuropathy (LHON): Gene Therapy Clinical Trial

IND NO.: 15941

IND SPONSOR: [REDACTED]

- LHON: Gene Therapy Clinical Trial is registered on the Clinical Trials.gov website (<http://clinicaltrials.gov>). Clinicaltrials.gov number: NCT02161380

2) **IRB Review History***

N/A

3) **Objectives***

Our goal is to test safety.

The **purpose** of this dose-escalation study is to assess the safety and tolerability of scAAV2-P1ND4v2 (abbreviated as AAV-ND4) gene replacement therapy in subjects confirmed with the G11778A mutation in mtDNA responsible for Leber's Hereditary Optic Neuropathy. Ocular and systemic toxicity will be assessed following vector administration to determine if there are adverse changes that may be associated with vector administration.

This first-in-man (FIM) clinical trial will assess safety, tolerability, and potentially efficacy of a single intravitreal injection in patient groups reflecting the acute, presymptomatic and chronic stages and manifestation of the LHON disease.

Aim 1. To Evaluate the Safety of AAV-ND4 in subjects with long-standing bilateral acuity loss (Group 1). Phase I will consist of an open-label, unilateral single-dose, intravitreal injection of AAV-ND4 per subject in a dose-escalation study investigating the safety of four vector doses (Low: 1.18×10^9 vg*, Medium: 5.81×10^9 vg*(*based on CHOP titers as recommended by FDA), High: 2.40×10^{10} vg and Higher: 1×10^{11} vg) in subjects with molecularly confirmed G11778A-mutated mitochondrial DNA. The bilateral chronic group will include patients with ≥ 12 months since onset in one eye and at least 6 months onset in the more recently affected eye. Both eyes must have acuity reduced to ≤ 35 letters. If both eyes have ≥ 12 months since onset, the eye with worse visual acuity will be

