Retinal detachment	Localized and intervention not indicated	Not resolving but intervention not yet indicated	Operative intervention indicated	Operative failure threatening ocular integrity*

*

For group III, due to the natural history of LHON where visual loss is expected in the asymptomatic eye, a vision-related SAE will be considered a decrease in acuity in the injected eye to 0.3 logMAR units (15-letter equivalent) worse than the worst acuity measured in the uninjected fellow eye at the current or any prior study visit.

Table 6-7: Systemic toxicity scale

Grade	Definition
1	Mild toxicity, usually transient, requiring no special treatment and generally not interfering with usual daily activities.
2	Moderate toxicity which may be ameliorated by simple therapeutic maneuvers, and impairs usual activities.
3	Severe toxicity which requires therapeutic intervention and interrupts usual activities. Hospitalization may or may not be required.
4	Life-threatening toxicity which requires hospitalization.

Evaluation of Secondary Endpoint – Visual Function Changes

Visual function will be quantified prior to and after vector administration in order to determine whether vector administration affects visual

function. The main measure of visual function will include best corrected ETDRS visual acuity.

10) Procedures Involved*

Method of Assigning Subjects to Treatment Groups:

Subjects enrolled in the study will be assigned to disease groups based on disease manifestation and screening evaluation. All subjects in the study will receive active treatment (one injection of scAAV2-P1ND4v2) at the Low, Medium or High dose as explained in section 6, Number of Subjects.

Study Visits:

Table 6-4 outlines the schedule of planned study evaluations. Subjects will be enrolled and undergo baseline assessments prior to Day 0. Study agent administration which will occur on Day 0 and details of the procedure are included below.

Table 6-4 Study Visit Summary Procedures

Time point	Baseline		Day								Year				
	B1	B2	0	1	7	3	6	9	1	2	3	1.5	2	3	4-10
Informed consent/assent	■														
Blood test for G11778A mutation	■														
History and physical exam	■			■		■		■			■				
Electrocardiogram, chest X-ray		■													
Pregnancy test	■	■													
Vital signs monitoring	■	■	■	■											
Hematology, chemistry, urinalysis	■		■	■	■	■	■	■	■	■	■	■	■	■	■
Coagulation Panel		■													
AAV antibody and specific reactivity (ASR) measurement	■			■				■			■				

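### Section 6's range of 3–18 and its 20/54/22% probabilities are three-dose figures and do not hold for Group I, which has four dose levels; Sections 10 and 12 also do not match Table 1

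*Combined protocol and SAP*

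**What the plan says.** Aim 1 in Section 3 describes Group I as a "dose-escalation study investigating the safety of four vector doses": Low, Medium, High and Higher.

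Table 1 in Section 6 plans these numbers:

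- Group I: 3 each at Low, Medium and High, plus 3 at Higher in a cohort shared with Group III.
- Group II: 3 each at Low, Medium and Higher.
- Group III: 3 each at Low and Medium, plus 3 at Higher in the shared cohort.

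The lead-in to the table reads: "For each group patient recruitment will consist of 3 cohorts, until the last cohort which will consist of both Group I and III individuals." The double-asterisk footnote opens the shared cohort "after the 3rd group II injection and 3 month safety period" and adds: "In this combined cohort, each of the 6 injections will be spaced at least 6 weeks apart."

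Below the table, Section 6 says a dose fails when 2 of 3 (or 6) injected eyes show the safety endpoint. It then says that "with three doses, the sample size could range between 3 and 18 for each group". With assumed event rates of 0.05, 0.25 and 0.5 it gives, again per group, N=9, 12 and 15 with probabilities 20%, 54% and 22%.

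Two later places differ from Table 1. Section 10 (Method of Assigning Subjects to Treatment Groups) says all subjects are injected "at the Low, Medium or High dose as explained in section 6, Number of Subjects". Section 12 (Evaluations of Efficacy in a phase I trial) repeats the dose table with no Group I subject at Higher and computes Group I power at N=9.

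**The concern.** The range and probabilities are offered for every group, directly below a table that gives one group a fourth dose level. If they hold only for three levels, the stated maximum for Group I is too low and its size probabilities belong to a different design.

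In a first-in-human trial the maximum number exposed is a figure that the ethics board, the regulator and the monitoring committee will read as a limit. The reader also finds two planned sizes for Group I and for the whole trial, and Group I power for an N that is not the one in Table 1.

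**Working it through.** **Inputs.** From Section 6: up to 6 eyes per dose, failure at 2 or more events, and rates 0.05/0.25/0.5. The cited algorithm is not in the documents, so its remaining details are inferred: 0 of 3 escalates; 1 of 3 adds three eyes; after a failure the next lower dose is filled to 6, one step only; the top dose is not filled after passing on three.

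**Formulas.** At event rate p:

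- pass on 3: a = (1−p)³
- pass on 6: e = 3p(1−p)² × (1−p)³
- fail on 3: s = 3p²(1−p) + p³
- fail on 6: f = 3p(1−p)² × [1 − (1−p)³]

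| p | a | e | s | f |
|---|---|---|---|---|
| 0.05 | 0.8574 | 0.1161 | 0.0073 | 0.0193 |
| 0.25 | 0.4219 | 0.1780 | 0.1563 | 0.2439 |
| 0.50 | 0.1250 | 0.0469 | 0.5000 | 0.3281 |

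**Reproducing the protocol (three doses).**

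- N=9: (a₁+e₁)s₂ + a₁a₂a₃ = 0.1521 + 0.0452 = 0.197
- N=12: (a₁+e₁)f₂ + a₁(a₂+e₂)s₃ + (passes with one dose expanded) = 0.2374 + 0.2572 + 0.0422 = 0.537
- N=15: e₁(a₂+e₂)s₃ + a₁(a₂+e₂)f₃ + (passes with two doses expanded) = 0.0348 + 0.1688 + 0.0121 = 0.216

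These round to 20/54/22%. The range is 3 (failure on the first three eyes) to 3 × 6 = 18. Of the variants tried, only this one matches all three figures.

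**Group I, four levels.** The maximum is 4 × 6 = 24 if Higher can expand, or 3 × 6 + 3 = 21 if Group I is held at 3 there. Probabilities need a fourth event rate, which the documents do not give. The table assumes 0.50 or 0.75:

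| Higher dose | Fourth rate | N=9 | N=12 | N=15 | N=18 | N>18 |
|---|---|---|---|---|---|---|
| can expand | 0.50 | 15.2% | 50.0% | 24.2% | 6.4% | 1.5% |
| can expand | 0.75 | 15.2% | 49.5% | 25.7% | 6.1% | 0.8% |
| held at 3 | 0.50 | 15.2% | 51.7% | 25.6% | 4.6% | 0.2% |
| held at 3 | 0.75 | 15.2% | 50.2% | 26.3% | 5.4% | 0.3% |

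On a flatter assumed curve (0.05/0.10/0.20/0.30), P(N>18) is about 6.7% with expansion and 0.6% without.

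**Group III.** It has three levels, but its Higher dose lies in the shared cohort. If that cohort can expand, 3–18 and 20/54/22% apply. If Group III is held at 3 there (2 or more events fill Medium to 6; otherwise it ends), the maximum is 6 + 6 + 3 = 15, and on the protocol's rates:

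- N=9: 0.1521 + a₁a₂ × 0.5 = 0.1521 + 0.1809 = 0.333
- N=12: 0.2374 + 0.2572 + (e₁a₂ + a₁e₂) × 0.5 = 0.595
- N=15: 0.0348 + e₁e₂ × 0.5 = 0.045

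**Group II.** It has three levels and its own Higher-dose cohort, so the stated figures fit.

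**Planned totals.** Table 1: Group I 3+3+3+3 = 12, Group II 9, Group III 9, total 30. Section 12: 9+9+9 = 27. Its Group II and III rows agree with Table 1; only the Group I row differs.

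**The case against.** The Section 6 sentence is conditional on three doses, the probabilities are offered as an example, and the lead-in to Table 1 sets the last cohort apart. That is fair, and the arithmetic is correct for what it assumes. But the result is then given for every group, and nothing supplies the Group I figure.

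The fourth event rate is assumed and the step-down rule is inferred. This limits the probabilities. It does not affect the maxima, which follow from at most 6 eyes per dose.

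The footnote says "Escalation from high dose group I to higher dose group II was previously approved", which suggests that Group I has already cleared High. A full four-level distribution would then partly describe known outcomes. This stands: the open question is what can happen at Higher.

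Three stronger readings are tempting and are not supported:

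- A reader might infer that Groups II and III break the Section 3 rule, "If none of the three subjects at a given dose level develops a major toxicity, the next cohort will receive the next higher dose", by going from Medium to Higher. On each group's own ladder in Table 1, Higher is the next dose after Medium, and the footnote gives the cross-group sequence. At most, Section 3 could cross-refer to it.
- A reader might put a figure on the Group I power that N=9 misses. The protocol names no test. A two-sided Fisher exact test with equal groups does not reproduce its figures (83% against a stated 92% at 28% versus 95%), so such a difference would not be reliable.
- A reader might infer that the fourth dose was never properly adopted. The syringe list in Section 10 and the patient ID code in Section 12 both include Higher, so the update was incomplete, not unintended.

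**Conclusion.** The point holds as a minor correction of stated figures. The 3–18 range and 20/54/22% are valid for three levels. They fit Group II, do not fit Group I, and fit Group III only if the combined cohort can expand. The stated Group I maximum is low by 6 (24) or by 3 (21).

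Exceeding 18 is unlikely: 0.2% to 1.5% at the protocol's rates with an assumed fourth rate of 0.5 to 0.75, and up to about 6.7% on the flatter assumed curve. Separately, Section 12 contradicts Table 1 on Group I (9 against 12) and on the trial total (27 against 30), and Section 10 omits a dose that all three groups receive. No effect on dosing decisions is shown.

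The maxima rest on the 6-eye limit in Section 6. The probabilities also rest on the inferred one-step rule and, for Group I, on the assumed fourth rate.

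**What to change.** - **Section 6:** limit 3–18 and 20/54/22% to Group II. State whether the combined Group I/III cohort at Higher can expand or is fixed at 3+3. Give the matching range for Group I (3–24 or 3–21) and for Group III (3–18 with the stated probabilities, or 3–15 with about 33/60/4.5% for N=9/12/15). Label any fourth event rate for Group I as an assumption.
- **Section 12, efficacy evaluation:** add Group I's 3 Higher-dose subjects to the table. Recompute Group I power at N=12 with the sponsor's own method, or say why only 9 count.
- **Section 10, assignment text:** add Higher to the dose list.
- **Optional:** cross-refer from the escalation rule in Section 3 to the Table 1 footnote.

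The cost is amendment text and a short recalculation. No planned patients are added; the stated Group I maximum rises by 3 or 6.
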